## Assessing the effect of nicotine reduction on ENDS users' addiction and exposure

### Background

The use of electronic nicotine delivery systems (ENDS) has reached epidemic levels among young people in the US. While estimates vary, ENDS have become the leading tobacco product used by young people in this country. ENDS heat and vaporize a nicotine-containing liquid to produce an inhalable aerosol mist. In addition to dependence-producing nicotine, ENDS emit other toxicants including aldehydes/carbonyls, a class of potent respiratory toxicants implicated in most non-cancer pulmonary diseases in cigarette smokers. Evidence indicates that young people using ENDS are likely to accelerate use, become nicotine dependent (ND), and initiate cigarette smoking. Epidemiological studies and market analysis moreover, suggests that "pod-mod" ENDS, JUUL in particular, had the biggest impact on the ENDS epidemic among young people. Unlike older ENDS generations, JUUL pioneered the use of nicotine salts which allowed to deliver high doses of nicotine in a smooth (protonated) form to users. Thus, addressing the addictiveness of ENDS through nicotine reduction (NR) can be a major regulatory strategy to reduce ENDS use among young people. In cigarette smokers, several observational studies and clinical trials have shown that smokers who switch to low nicotine cigarettes reduce daily nicotine intake, smoke fewer cigarettes, report lower dependence, and show higher trends in quitting. Similar patterns are expected in ENDS users, as our preliminary study of NR in young JUUL users shows that it leads to decreased satisfaction, dependence suppression, and intention to use in the future. However, reducing ENDS nicotine levels carries the risk of compensatory puffing and increased exposure. Evidence suggests that such compensation is dose and ND related, where very low nicotine products and beginning users are likely to have minimal compensation. Accordingly, assessing the potential role of NR regulations to reduce ENDS use and addiction requires standardized comparisons involving a range of NR levels and ENDS users at different stages of their use trajectory. It also requires assessing a wide array of outcomes to evaluate the effects of compensatory puffing on exposure to key pulmonary toxicants. These goals can be achieved by applying within-between subject comparisons to assess responses to a range of NR levels (partial vs. total) in ENDS users with different use profiles. Our team has pioneered the use of clinical and analytical lab methods to provide rapid and robust evidence about promising tobacco product manipulations for regulatory purposes (e.g. flavor). We plan to use these methods to compare among ENDS (e.g. JUUL) users the effect of 5% nicotine concentration, 3% (partial NR) or 0% (total or nicotine-free) NR on dependence, satisfaction, puffing behavior, clinical outcomes, and toxicant exposure. Our overarching hypothesis is that NR for ENDS will be associated with less satisfaction, withdrawal suppression, and intention to use and that such an effect will be more pronounced in total vs. partial NR. Our secondary hypothesis is that with very low nicotine ENDS and low dependence users, NR will cause minimal compensatory puffing and increased exposures. We will recruit current ENDS users (n=120; 21-35 yrs), for a 2X2 within- subject factorial crossover lab study. The nicotine conditions (5%, 3%) or (0%, 5%) x 2 time (pre-post) are the within-subject factors. A follow-up call at 3-months post-lab will be made to assess nicotine preference and changes in ENDS use.

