
We intend to answer 3 main regulatory questions that are directly responsive to this RFA's focus under Addiction; "Impact of changes in tobacco product characteristics (e.g. nicotine formulation) on dependence"; 1) is NR a promising regulatory option to reduce ENDS addictiveness and use; 2) what is the effect of partial vs. total NR on compensatory puffing and exposures; and 3) what is the effect of NR on ENDS users at different stages of use.

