## **Study Aims**

Aim 1. To assess the subjective and clinical effects of NR on ENDS users. Participants will undergo 2 ENDS use sessions that are preceded by 12-hour abstinence, with session order counter-balanced to mitigate order and carry-over effects. This study will focus on pre-post-use assessment of craving, withdrawal, satisfaction, intention to quit or use in the future, lung functions (e.g. FEV1 % predicted; FEV1/FVC, CO diffusing capacity-DLCO), and symptoms (e.g. dry mouth, eye irritation, palpitation, nausea). This aim will show ENDS users' response to NR on product satisfaction, dependence, lung functions and symptoms.

Aim 2. To assess puffing behavior in response to NR. Under the same protocol, puff topography (e.g. puff volume, puff frequency, duration) will be assessed continuously during the 2 sessions, while plasma nicotine will be measured pre-post sessions to assess nicotine boost and its correlation to puffing parameters. This aim will help understand users' compensatory puffing in response to NR and its effect on plasma nicotine.

Aim 3. To assess exposure to toxicants associated with NR. We will measure toxicant emissions (14 aldehydes) in the analytical lab using a smoking robot that reproduces the puff-by-puff behavior (playback) of each participant for all two nicotine conditions (Aims 1, 2). This aim will reveal how compensatory puffing behavior in response to NR influences acute exposure to pulmonary toxicants.

The proposed studies will give clear evidence on the potential of NR regulations to limit the addictiveness and use of ENDS, and to help predict any potential side effects of NR on ENDS users.

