## **Study Design**

This study is divided into 2 parts (studies), whereby the first part will be 2X2 comparing NJOY 5% and 3% to test the effects of partial nicotine reduction, and the second part will be using the NIDA Standardized Research Electronic Cigarette (SREC) for Clinical Research 5% and 0% (placebo), to test the effect of the total reduction using the same pods and juices from the same manufacturer.

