Screening, and informed consent: Individuals who are identified as potentially eligible based on the phone screening will be asked to attend an onsite-screening, which will involve assessment of inclusion/exclusion criteria, physical examination, COVID-19 screening, and urine pregnancy testing for women. Prior to screening, potential participants will undergo a review of the study and consent procedures to ensure that they understand the study, its risks/benefits, and their rights as research participants. Consented (written) individuals will then undergo a physical examination conducted by the research nurse, who will have access to an on-call Medical Monitor (physician) in case of concern or for consultation at any point of the study as it is the standard practice in our lab. Successfully consented participants will be scheduled for their 1st session and asked to abstain from all tobacco/nicotine use 12 hours prior to it.

Sample size. All power calculations were performed with PASS19 (PASS, 2019). We built our calculation of the sample size for this study based on our preliminary study of the effect of NR on subjective (e.g. craving, urges) and puff topography measures (pls. see Preliminary Studies), where medium effect size (Cohen's  $f=0.2$ ) depending on nicotine condition was detected. Expecting a maximum 20% loss due to noncompliance with abstinence or study protocol (Vargas-Rivera et al., 2020), this study will include a dropout inflated sample of 150 ENDS users. Using repeated measures ANOVA F-test with 2 within and 1 between factors, a total dropout adjusted sample size of 120 (2X60) participants will have at least 80% power to detect small to medium-size effect (Cohen's  $f=0.1-0.2$ ) or larger for 2 within-subject (NR condition and time) and 1 between subject (use frequency) factors, as well as their interactions at 0.05 level of significance, assuming sphericity and a moderate correlation (0.5) among repeated measures (Cohen, 1988).

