Experimental protocol. Participants from each frequency group will be randomly assigned to one of the nicotine concentration conditions and attend the lab for two, ~2-h sessions, separated by a 48-h washout period, and differ by nicotine concentration (3%,5%) or (0%, 5%). Session order will be counterbalanced to mitigate order and carry-over effects. At the beginning of the 1st session, participants will provide consent, complete demographic and personal information including age, sex, socioeconomic status, race/ethnicity, and detailed tobacco/nicotine use history. Participants will get familiarized with the study procedures, measures, and they will be given time to adapt to the lab. After adaptation, continuous measurement of physiological responses begins, and 10 ml of venous blood is sampled, lung function tests will be conducted, and participants are asked to respond to subjective measures (pls. see below Outcome Measures). Participants will inhale on their session ENDS ad libitum for up to 60 minutes (as in Vargas-Rivera et al., 2020). At the end of the ENDS use period 10 ml of blood will be sampled, lung function tests repeated, and subjective measures assessed. The session will terminate 30 minutes after the last puff, and the 2nd session is scheduled. A follow-up phone call at 3-month post-study will be made to evaluate nicotine preferences and changes in ENDS and tobacco use.

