## **AIM 1: To assess the subjective and clinical effects of nicotine reduction on ENDS users.**

Objective and hypothesis. This aim will help understand users' response to NR and how it will influence their product satisfaction, nicotine dependence, intention to quit or use in the future, lung functions, and clinical symptoms. We hypothesize that NR will be associated with less satisfaction, withdrawal suppression, and intention to use in the future and that such an effect will be more pronounced in total compared to partial NR and in high compared to low-frequency users.

Outcomes. We will utilize our clinical lab model to study the effect of NR on the following outcomes assessed according to the plan described in Table 2. All assessments will be based on instruments that are standard in clinical lab studies of addictive behaviors modified for the ENDS we plan to use (Vargas-Rivera et al., 2020). Participants will use a tablet to respond to these measures using RedCap.

**Outcomes.** We will utilize our clinical lab model to study the effect of NR on the following outcomes assessed according to the plan described in Table 2. All assessments will be based on instruments that are standard in clinical lab studies of addictive behaviors modified for the ENDS we plan to use (Vargas-Rivera et al., 2020). Participants will use a tablet to respond to these measures using RedCap. Briefly, we will assess;

1. Demographic and baseline characteristics; including age, race, sex, and reasons for ENDS use. Other characteristics will include the frequency of ENDS use, and the history of other tobacco/nicotine products use (Amato, Boyle & Levy, 2016; Zavala-Arciniega et al., 2019; Vargas-Rivera et al., 2020).
2. Dependence measures including; 1) *Use satisfaction* (Modified Cigarette Evaluation Questionnaire (mCEQ) (Arger et al., 2017); 2) *Dependence* (Questionnaire of Smoking Urges-brief and the Minnesota Nicotine Withdrawal Scale, Penn State Electronic Cigarette Dependence Index (Ben Taleb et al., 2018; Foulds et al., 2015; St Helen et al., 2017); 3) *Puff sensory effects* (Duke Sensory Scale, (Malson & Pickworth, 2002)).

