## **AIM 3: To assess exposure to toxicants associated with nicotine reduction.**

**Objective and hypothesis:** This aim will help elucidate how compensatory puffing behavior in response to NR affects exposure to pulmonary toxicants. *We hypothesize that partial but not total NR will be associated with compensatory puffing behavior that will, in turn, lead to greater exposure to toxicants.*

**Analytical methods.** The analytical assessments will be conducted at the AUB Aerosol Research Laboratory (ARL). The ARL is equipped with two digital playback smoking machines necessary for Aim 3. These two machines, developed and tested by our team at AUB, are to our knowledge unique to this setting and are not available in any other laboratory. The proposed work in Aim 3 is built on the ARL framework and infrastructure for aerosol generation, sampling, and chemical analysis.

**Aerosol generation and sampling:** The deidentified puff topography data will be shared via Microsoft Sharepoint between FIU and AUB Aerosol Lab, thus, all communication will be encrypted between client and server using SSL 2048 bit keys. Access to the lab and data will be granted only by permission of Drs. [name] (PI), and [name] (local PI at AUB).

Once the puff topography files have been received by the ARL, we will use ALVIN (Aerosol Lab Vaping Instrument) (Talih et al., 2015, 2017) to draw aerosols from the ENDS devices, for each of the 240 topography sessions. For each session, ALVIN will be programmed to reproduce the puff topography data generated in the clinical lab. The generated aerosol will be drawn through a Gelman type A/E 47mm glass fiber filter followed by a 2,4-dinitrophenylhydrazine-coated silica cartridge (type LpDNPH H10) cartridge, for nicotine and aldehydes quantification, respectively (see Talih et al., 2015, 2017; El-Hellani et al., 2018 for more detail). The pods (e.g. JUUL) and batteries will be shipped from the same batch as those used at FIU to minimize biases. A new pod will be used for every session. Each pod will be pre-conditioned before sampling by drawing 15 4-second puffs at 1 LPM using ALVIN. We will use a quality assurance protocol and ENDS electrical performance tester developed at the ARL to ensure that each battery and pod are within tolerance (Talih et al., 2019, 2020b).

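### Total versus partial nicotine reduction is a regulatory question and a stated hypothesis, but no planned analysis or power statement contains a term that compares the two reduction effects

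*Combined protocol and SAP*

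**What the plan says.** **The question.** The Background lists as regulatory question 2 "what is the effect of partial vs. total NR on compensatory puffing and exposures". Its overarching hypothesis is that "such an effect will be more pronounced in total vs. partial NR". Aim 1 repeats this: "such an effect will be more pronounced in total compared to partial NR". Aim 3 hypothesises that "partial but not total NR will be associated with compensatory puffing behavior that will, in turn, lead to greater exposure to toxicants". The Background also says the goals can be met by comparing partial with total NR both within and between participants.

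**The design.** Study Design has two parts. The first compares NJOY 5% with 3%; "the second part will be using the NIDA Standardized Research Electronic Cigarette (SREC) for Clinical Research 5% and 0% (placebo"). The Experimental protocol paragraph says "Participants from each frequency group will be randomly assigned to one of the nicotine concentration conditions", so each person supplies one pair of sessions.

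**The analysis.** Under Statistical analysis:
- The primary ANOVA for each outcome has two within-subject factors: the concentration pair (5% and 3%, or 0% and 5%) and time.
- The mixed-model extension names personal attributes (sex, education, race, SES), and sex has a pre-planned interaction.
- A two-sample t-test is listed for a between factor.
- Aim 3 uses a one-way ANOVA for the effect of NR on aldehydes, plus regressions on topography.

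**The power statement.** The Sample size paragraph covers "2 within-subject (NR condition and time) and 1 between subject (use frequency) factors" and their interactions. Study part is not among them.

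**The concern.** Each of these hypotheses concerns a difference between two effects: the change from 5% to 0% against the change from 5% to 3%. A model with concentration pair and time estimates each change but does not compare them. The answer to regulatory question 2 could then rest on two p-values read side by side. One significant and one non-significant result do not show that two effects differ. The second half of the Aim 3 hypothesis, no effect under total reduction, would rest on a non-significant result alone.

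The stake is that a chance difference in significance between the parts could be reported as an effect of reduction depth.

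**Working it through.** **1. The plan's own figures.** Dropout: 120/(1 − 0.20) = 150, as stated. For power, use a noncentral F with 1 df and λ = N·m·f²/(1 − ρ), where m is the number of measurements per person and ρ = 0.5. With N = 120 and m = 4 (two sessions, pre and post), f = 0.1 gives λ = 9.6 and power 87% for within-subject effects and their interactions. For the between factor, λ = N·m·f²/(1 + (m − 1)ρ); f = 0.2 gives λ = 7.68 and power 78.5%. The stated range of f = 0.1–0.2 at 80% is therefore essentially reproduced, with all 120 people in one model and four measurements each.

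**2. Inputs for each part.** Aim 3 has 240 topography sessions = 120 people × 2. An equal split gives 60 per part. This is an assumption: the 2X60 in the Sample size paragraph could mean two parts or two frequency groups. ρ = 0.5 and two-sided α = 0.05 follow the plan (two-sided is assumed).

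**3. Chance discordance when both reductions have the same true effect.** If p is the power in one part (n = 60, 59 denominator df), partial significant with total not significant has probability p(1 − p), because the parts contain different people.

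| Outcome type | f | λ | p | p(1 − p) |
|---|---|---|---|---|
| Once per session (m = 2) | 0.1 | 2.4 | 0.332 | 0.22 |
| Once per session (m = 2) | 0.2 | 9.6 | 0.862 | 0.12 |
| Pre and post, both sessions (m = 4) | 0.1 | 4.8 | 0.577 | 0.24 |
| Pre and post, both sessions (m = 4) | 0.2 | 19.2 | 0.991 | 0.01 |

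Once-per-session outcomes are topography, aldehydes and, from Table 2, the post-only satisfaction, visual analogue and sensory scales. The mirror pattern (total significant, partial not), which suits the Aim 1 hypothesis, has the same probability. One pattern or the other therefore occurs twice as often: for m = 4, 49% at f = 0.1 and 2% at f = 0.2. For ρ from 0.3 to 0.7 the once-per-session figure runs from 0.19 to 0.25 at f = 0.1, and from 0.20 down to 0.02 at f = 0.2.

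**4. What the direct contrast can detect.** Take an effect in one part and none in the other, 60 per part, 118 df.
- *Once per session.* SD of the paired difference = √(2(1 − 0.5)) = 1.00 SD; SE of the contrast = √(2/60) = 0.183; 95% CI half-width = 1.98 × 0.183 = 0.36 SD. The gap is 2f SD: 0.2 SD at f = 0.1 (power 19%) and 0.4 SD at f = 0.2 (power 58%). Power of 80% needs a gap of 0.52 SD.
- *Pre-post change.* SD = √(4(1 − 0.5)) = 1.414 SD; SE = 1.414 × 0.183 = 0.258; half-width = 0.51 SD. The gap is 4f SD: 0.4 SD (power 34%) and 0.8 SD (power 87%). Power of 80% needs a gap of 0.73 SD.

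At f = 0.2, 80% power needs about 100 per part once per session and 51 per part for pre-post change. For ρ from 0.3 to 0.7, power at f = 0.2 runs from 45% to 80% once per session and from 74% to 98% for pre-post change.

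**The case against.** The strongest reply is that the plan does intend the comparison. The Background speaks of within- and between-participant comparison of partial with total reduction, and Statistical analysis already provides for a mixed model. That stands: the framework exists, and what is missing is a named term. But a stated intention does not define a test, and study part is not among the covariates listed.

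A second reply is that the between factor in Statistical analysis might be study part. The same paragraph expects randomisation to reduce group differences, and use frequency cannot be randomised. Yet it also expects groups to differ on past 30-day use, which points to frequency, and the Sample size paragraph names frequency. The wording is ambiguous. A two-sample t-test would supply the contrast only if applied to within-person differences, which is not stated.

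Third, nowhere does the plan say that partial and total will be judged by comparing p-values. That is correct. The discordance figures describe what could happen if they were; they do not describe a planned step.

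Fourth, at f = 0.2, the preliminary effect size the plan cites, the risk for pre-post outcomes is only about 1% per pattern. The Background also labels a closely related statement on minimal compensation with very low nicotine a secondary hypothesis. Both points moderate the weight. Neither removes the gap, because total versus partial is also in the overarching hypothesis and regulatory question 2.

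**Conclusion.** The point holds: the comparison is a declared goal, and as written no analysis tests it or gives its power. The risk is material for once-per-session outcomes (12% at f = 0.2, 22% at f = 0.1) and for pre-post outcomes at f = 0.1 (24%), and negligible for pre-post outcomes at f = 0.2 (1%). These figures assume 60 per part, correlation 0.5 and equal true effects. It should be fixed before analysis. Estimates of each reduction against its own 5% session remain valid, and regulatory questions 1 and 3 do not depend on this contrast.

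A reader might infer three stronger things that the documents do not support:
- *That the trial as a whole is underpowered.* The stated power is essentially reproduced on the plan's own terms; what is absent is power for this contrast.
- *That the Aim 3 ANOVA pools 5%, 3% and 0% across products.* Pooling is possible but not established, so no error rate is claimed for it.
- *That participants are not randomised between the parts.* The Experimental protocol paragraph reads as random assignment to a concentration pair within frequency group.

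**What to change.** - Analyse both parts in one mixed model with participant as a random effect. Name part x condition (part x condition x time for pre-post outcomes) as the test of total versus partial, each part referenced to its own 5% session, with estimate and 95% CI.
- Use the same paired model for aldehydes in place of the one-way ANOVA.
- Do not conclude that total reduction has no effect from a non-significant result; report the CI for the SREC 5%-to-0% effect.
- State that the contrast combines reduction depth with product (NJOY versus SREC), which this design cannot separate.
- State the power of the contrast for each outcome type, using the figures in step 4 or the sponsor's own, and say what 2X60 and the between factor refer to.

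The cost is SAP wording and one model term, with no new data. The downside is limited sensitivity: the once-per-session contrast may have to be reported as an estimate with a wide interval rather than as a decisive test.

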## **AIM 2: To assess the puffing behavior in response to nicotine reduction.**

**Objective and hypothesis.** This aim will help understand users' compensatory puffing behavior in response to NR and its effect on plasma nicotine as the main substance sustaining addiction to ENDS. *We hypothesize that NR-related compensatory puffing will be more pronounced in high vs. low-frequency users.*

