Demographic data will be examined and compared to determine if there are significant between-group differences on measures that may be related to study outcome (some differences are expected due to design such as past 30-day ENDS use) though these are expected to be minimized due to randomization. Unexpected between-group differences will be considered as potential adjustment covariates in the primary analysis (Evans et al., 2006). We will generate descriptive statistics which include means, standard deviations, frequencies, and proportions depending on the scale of the outcome by NR factor, time and group assignment. Univariate comparisons of the outcomes by the mentioned conditions will consist of repeated measures ANOVA and paired t-test (for 2X2 within factors) and two-sample t-test for between factor, or their non-parametric equivalents (Wilcoxon signed-rank test and Friedman test for within factors and Wilcoxon Mann-Whitney U test for between factor) if the parametric assumptions are not met. ANOVA will be followed by multiple comparisons with Bonferroni adjustments for multiplicity. Analysis of categorical outcomes will involve a chi-square test of independence for between factors or McNemar's test for paired proportions. The primary analysis of each outcome will involve analysis of variance with two within-subject factors (nicotine concentration: (5%, 3%) or (0% 5%)) and time (pre-post-use). This approach will be extended into a mixed-effects linear regression model to adjust or study the effects of personal attributes such as sex, education, race, and SES. Furthermore, we will consider clinical/physiologic factors such as lung function and respiratory symptoms in a similar modeling approach described above, as a function of experimental factors and demographic covariates, in order to quantify the harm or disease risk. In a case of a non-linear relationship between these factors, we will apply outcome transformations or use non-linear splines to accurately describe these outcomes as a function of

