mentioned covariates. Given the known sex-related differences in nicotine dependence (Benowitz et al., 2006), to assess if sex has any effect on the results, it will be considered as a covariate and we will test the pre-planned interaction with it to determine the heterogeneity of the study outcomes by sex as well as potential differential effects. Similarly, for categorical outcomes we will apply generalized linear models and estimating equations with the same main effects as described above, modeling within factors as random effects. We will test for the carry-over effect statistically and will control for it when testing for the primary factors (Senn, 2002).

For Aim 3, we will use a one-way ANOVA to test the effect of NR on aldehyde emissions and multiple linear regression analysis to assess the influence of puff topography data (puff volume, duration, number, and interpuff interval) on aldehyde emissions. Additionally, we will measure the relation between the plasma nicotine levels obtained in the clinical lab and measured nicotine yields obtained in the analytical lab using linear regression. Significance levels will be adjusted for violations of the sphericity assumption using Huynh-Feldt corrections (Keppel, 1991). All differences will be considered significant at the alpha level of 0.05 using adjusted p-values where appropriate. Due to the nature of laboratory data collection, missing data is rare and it usually occurs due to instrument malfunction. All data are collected and checked for completeness by laboratory staff. In the case of missing data, which we expect to be minimal, we will use a regression model based on multiple imputations with all available outcome data, demographic, and clinical variables as predictors. This will be carried out in 25 random repetitions under missing at random assumption, analyzed using methods described above and results will be combined to produce unbiased overall estimates and standard errors of the experimental conditions. As a sensitivity analysis completers results will be compared with multiple imputation results.

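### The plan predicts minimal or no compensatory puffing under some nicotine conditions but gives only tests of difference, so it has no criterion by which those claims could be concluded

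*Combined protocol and SAP*

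**What the plan says.** Two stated hypotheses contain a claim of little or no effect.

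- Aim 3, Objective and hypothesis: "partial but not total NR will be associated with compensatory puffing behavior", with greater toxicant exposure expected to follow from the compensation. The part about total reduction is a claim of no effect.
- Background, secondary hypothesis: "with very low nicotine ENDS and low dependence users, NR will cause minimal compensatory puffing and increased exposures". Minimal is not given a number.

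The Statistical analysis section sets out how outcomes will be judged.

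- "The primary analysis of each outcome will involve analysis of variance with two within-subject factors", namely nicotine concentration and time, with concentration being either the 5%/3% pair or the 0%/5% pair.
- For Aim 3, "we will use a one-way ANOVA to test the effect of NR on aldehyde emissions".
- "All differences will be considered significant at the alpha level of 0.05 using adjusted p-values where appropriate".

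The Study Design section splits the trial into two parts: NJOY 5% against 3% (partial reduction) and SREC 5% against 0% (total reduction). The sample size paragraph concerns power to detect effects. No section gives an equivalence or non-inferiority margin, a rule based on a confidence interval, or a test of whether the nicotine effect differs between the two parts.

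**The concern.** A test of difference can support the claim that compensation occurs. Its failure cannot support the claim that compensation is absent or minimal, because a real rise and a noisy estimate give the same non-significant result. The pattern of partial but not total has a second weakness. With no contrast between the parts, a reader can only set one p-value beside another, and one significant and one non-significant result do not show that the two effects differ.

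This matters because the Background itself names compensatory puffing and increased exposure as the risk of nicotine reduction, and the second regulatory question concerns partial against total reduction on exactly these outcomes. With a failed test as the only evidence, lower sensitivity makes a reassuring conclusion easier to reach. A nicotine-free product could then be described as free of extra aldehyde exposure because the study missed it.

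**Working it through.** **Inputs.** From the sample size paragraph: 120 analysed, written as 2X60; 150 enrolled after 20% loss; Cohen's f = 0.1 to 0.2; correlation 0.5; alpha 0.05. Assumed: 2X60 means 60 in each part (it could mean frequency groups), and tests are two-sided.

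**The plan's own figures.**

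- Inflation: 120/(1 − 0.20) = 150, as stated.
- Power for a two-level within-person effect: noncentrality λ = f² × N × 2/(1 − 0.5). With N = 120, f = 0.1 gives λ = 4.8 and power 58%; f = 0.13 gives 81%; f = 0.2 gives λ = 19.2 and power 99%.
- With 60 in one part, f = 0.2 gives λ = 9.6 and power 86%.

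The stated 80% is therefore broadly right for within-person effects, though not for every effect at f = 0.1.

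**Scale.** With correlation 0.5, the SD of the paired difference is √(2 × (1 − 0.5)) = 1 outcome SD. For two levels d = 2f, so the plan's f = 0.2 is 0.4 SD and f = 0.1 is 0.2 SD.

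**Chance that a real rise is non-significant.** Paired t-test, noncentrality d√n; critical t is 2.001 for n = 60 and 2.045 for n = 30. The last column is the chance of partial significant and total not when both parts (60 each) share the same true rise, which is power × (1 − power).

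| True rise | Missed, n = 60 | Missed, n = 30 | Partial significant, total not |
|---|---|---|---|
| 0.2 SD | 67% | 81% | 0.332 × 0.668 = 22% |
| 0.3 SD | 37% | 64% | 0.628 × 0.372 = 23% |
| 0.4 SD | 14% | 44% | 0.862 × 0.138 = 12% |

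The n = 30 column illustrates a low-use subgroup within one part. The documents give no such number.

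**Precision.** The 95% confidence interval half-width is 2.001/√60 = 0.26 SD, or 2.045/√30 = 0.37 SD.

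**One-way ANOVA for aldehydes.** If it ignores pairing, it uses a standard error of √(2/60) SD where the paired one is √(1/60). By simulation at n = 60 and correlation 0.5, it misses 0.2 SD in about 89% of trials and 0.3 SD in about 68%.

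**What a confidence-limit rule would achieve.** The documents give no margin M, so a range is shown. With no true difference, the chance that the upper 95% limit lies below M is the upper tail of a noncentral t with noncentrality M√n.

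| Margin | Met, n = 60 | Met, n = 30 |
|---|---|---|
| 0.2 SD | 33% | 18% |
| 0.3 SD | 63% | 36% |
| 0.4 SD | 86% | 56% |

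**Partial against total.** The difference of two mean paired differences, 60 each, has standard error √(2/60) = 0.183 SD. The 95% half-width is 1.98 × 0.183 = 0.36 SD. Power is about 37% for a difference of 0.3 SD and 58% for 0.4 SD.

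**The case against.** The strongest reply is that nowhere does the plan say a p-value above 0.05 will be read as support for minimal or no compensation. That is correct. A reader might infer that the investigators intend to prove absence from a failed test, but the documents say only when a difference counts as significant. What stands is narrower: the plan states the claims and supplies no criterion for them.

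Other replies, and what remains of each:

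- **All the compensation hypotheses might be thought to fail.** They do not. Aim 2 predicts that "NR-related compensatory puffing will be more pronounced in high vs. low-frequency users", which is an ordinary difference hypothesis, and the analysis fits it. The partial half of the Aim 3 hypothesis is also unaffected.
- **The plan has more than p-values.** It has mixed models, and it promises combined estimates and standard errors after imputation. Intervals could be built from these, but no rule says how they would bear on a claim of minimal compensation.
- **The regulatory question asks for the size of an effect, not its absence.** This is fair, and it favours reporting intervals.
- **At the plan's own medium effect the problem is smaller.** At 0.4 SD and n = 60 the miss rate is 14% and the misleading pattern 12%. The larger figures belong to rises of 0.2 to 0.3 SD, of which 0.2 SD is the lower end of the range the plan says it can detect.
- **The subgroup figures are conditional.** The Background speaks of low dependence and Aim 2 of low frequency, and neither comes with a number. The n = 30 results are illustrative only.
- **The remedy has limits.** A margin below 0.4 SD is often not met even with no true effect. With a 0.4 SD margin, a true 0.2 SD rise would still pass 33% of the time at n = 60. The contrast between parts is imprecise and confounded with product.

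**Conclusion.** The concern holds in this form: the plan hypothesises minimal compensation, and compensation under partial but not total reduction, yet provides only tests of difference within each part and no contrast between them. A failed test would be weak evidence. At n = 60 it occurs in 67%, 37% or 14% of trials when the true rise is 0.2, 0.3 or 0.4 SD. The hypothesised partial/total pattern arises in 22%, 23% or 12% when the two effects are in fact equal. An unpaired ANOVA, or multiplicity adjustment where it is applied, would raise the miss rates.

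These figures rest on 60 per part, the plan's correlation of 0.5, and a paired two-sided test. The choice of margin belongs to the investigators. Whether a failed test can establish absence is a question of validity rather than preference, and the plan should settle it before the data are analysed.

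**What to change.** Amend the Statistical analysis section in two places.

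1. For puffing and for aldehyde emission, report the reduced-minus-5% difference with its 95% confidence interval in each part, using the within-person pairing. State that no or minimal compensation will not be concluded from a non-significant test. The wording will be 'not shown' unless the upper confidence limit lies below a margin that the investigators fix before analysing the data.
2. Judge partial but not total by the difference of the two within-person contrasts with its 95% confidence interval, not by comparing p-values. State that this contrast is confounded with product, since partial reduction is studied with NJOY and total reduction with SREC.

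The cost is wording and, if the claim of minimal compensation is to be kept, a margin for each of the two outcomes. No extra data are needed. The price is that the claims become harder to make, as the margin and contrast figures above show. If no margin can be justified, the intervals and the 'not shown' wording are enough.
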